9.4.1.2 Main Analytical Approach

A mixed model for repeated measures (MMRM) with parameters for treatment group, visit (excluding Week 20), baseline vIGA score, baseline relevant questionnaire score and the interaction for treatment*visit will be used.

Treatment will consist of 4 levels (all placebo, cohort 1 EDP1815, cohort 2 EDP1815, cohort 3 EDP1815). Baseline vIGA will consist of 3 levels (2, 3 and 4).

As described in [Section 9.2](#), any baseline covariates fitted into the primary analysis model will also be fitted in the models for these endpoints.

An unstructured covariance structure will be used. If there are issues with model convergence, other covariance structures may be considered (e.g. compound symmetry).

Distributional assumptions underlying the model used for analysis will be examined by a normal probability plot of the residuals and a plot of residuals versus the fitted values (i.e. checking the normality assumption and constant variance assumption of the model respectively) to gain confidence that the model assumptions are reasonable.

Least squares mean estimates and their 95% confidence intervals (CI) will be presented for the endpoint value at each visit. Treatment differences between each EDP1815 group (including cohorts 2+3 EDP1815 and all EDP1815 groups) and the pooled placebo group will be estimated using LS mean differences, 95% CI and p-values. Pairwise treatment differences between EDP1815 groups will be estimated with LS mean differences and 95% CI.

Least square mean (95% CI) estimates will be plotted against visit. Least square mean (95% CI) treatment differences between each EDP1815 treatment group and the pooled placebo group will also be plotted against visit. Waterfall plots at Week 16 will be presented as panels for individual treatment groups.

In addition, for the secondary endpoints based on the EASI, vIGA and PP-NRS only, a supportive analysis will be performed using the EDPS2.

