11.4.4. Analysis of Secondary Estimands

Continuous secondary estimands will be analyzed using a mixed model for repeated measures (MMRM) with parameters for treatment group, visit, baseline IGA score and relevant baseline score and the interaction for treatment*visit.

For the potential covariates of body mass index, gender, race and region: those covariates found to be significant in the primary analysis will be included in all models regardless of significance in order to ensure comparability of the models.

Least squares mean estimates and their 95% confidence intervals (CI) will be presented for the endpoint value at each visit. Treatment differences between each EDP1815 group and the pooled placebo group will be estimated using LS mean differences, 95% CI and p-values. Pairwise treatment differences between EDP1815 groups will be estimated with LS mean differences and 95% CI.

Least square mean (95% CI) estimates will be plotted against visit. Least square mean (95% CI) treatment differences between each EDP1815 treatment group and the pooled placebo group will also be plotted against visit.

Response estimands will be analyzed with a generalized linear mixed effects model with a logit link function. Treatment, visit, baseline IGA and the appropriate baseline questionnaire score will be included as parameters together with the treatment*visit interaction. Odds ratios with 95% CIs and p-values for each EDP1815 group compared to the relevant pooled placebo group at each visit will be presented. Odds ratios and 95% CIs will be presented for any comparisons between two EDP1815 treatment groups.

In the event that there are no responders in one of the treatment groups at a visit, data from that visit will be excluded from the model and only summary statistics will be produced showing the number and percentage of responders at that visit.

Count estimands will be analyzed with a Poisson regression model fitted with treatment and baseline IGA as covariates. An offset of log (days in study) will also be included in the model to account for any data from participants who withdrew early from the study. If the distribution of the count data suggests over-dispersion and/or zero inflation, then other models including the negative binomial or zero-inflated Poisson model may be considered.

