11.6. Handling of Dropouts or Missing Data

Unless otherwise specified, missing data will be considered as missing at random and will be accounted for using mixed models for repeated measures, with all time points collected for the relevant endpoint included in the model.

Otherwise, missing data will not be imputed.

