11.8. Determination of Sample Size

Cohorts 1-3

The sample size was calculated using the assumption that data from the placebo participants in the three cohorts can be pooled prior to comparison with the EDP1815 treatment groups. No adjustments for multiple testing have been made.

The primary efficacy endpoint is the achievement of EASI-50 at Week 16. The pooled placebo response rate is estimated to be approximately 25% and a doubling of this to 50% for EDP1815 would be considered as clinically meaningful.

Using a two-sided test at the 5% level of significance, 58 participants in each treatment group would give 80% power to detect a difference in one of the EDP1815 cohorts compared to the pooled placebo group. There would also be more than 90% power to compare the pooled EDP1815 6.4×10^{11} daily dose or all the EDP1815 group to the pooled placebo group.

Under the assumption of a 20% drop-out of participants prior to Week 16 this will require a total of at least 73 participants to be enrolled in each treatment group. In order to allow for the 3:1 randomization in each cohort this has been adjusted to 75 participants per treatment group to give a total of 300 participants recruited. With 75 EDP1815 participants and 25 placebo participants in each of the three cohorts.

Cohort 4

Using the same assumptions relating to the placebo rate, clinically meaningful difference, significance level, and drop-out rate as above for Cohorts 1-3, approximately 70 participants are required in each of the EDP1815 8.0×10^{10} and Cohort 4 Matched Placebo groups to provide approximately 80% power in detecting a difference between EDP1815 and placebo in Cohort 4.

In order to allow 50% of the placebo control group to be concurrent controls and 50% to be historic matched controls from Cohorts 1-3, a 2:1 randomization will be used to enroll 70 EDP1815 8.0×10^{10} subjects and 35 placebo participants to Cohort 4.

If sensitivity analyses indicate that pooling of the Cohort 4 placebo group with the Cohort 1-3 matched placebo data is inappropriate, then the power of the comparison between the Cohort 4

EDP1815 and placebo groups is approximately 65% if only Cohort 4 placebo participants could be used in the treatment comparisons.

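### The MMRM for continuous secondary endpoints has no baseline-by-visit terms; adding them is cheap and may reduce the Week 16 standard error for absolute change by roughly 0–10%

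*SAP*

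**What the plan says.** Protocol 11.4.4 gives the MMRM parameters as "treatment group, visit, baseline IGA score and relevant baseline score and the interaction for treatment*visit". SAP 9.4.1.2 repeats them ("baseline vIGA score, baseline relevant questionnaire score and the interaction for treatment*visit will be used") and treats baseline vIGA as a three-level factor. It adds any covariates carried over from the primary model, again as main effects. On the residuals it says "An unstructured covariance structure will be used", with simpler structures allowed if the model does not converge. No baseline-by-visit term appears in either document, and the Cohort 4 addendum refers back to the main SAP for model specifications.

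SAP 9.4.1.2 leaves Week 20 out of the model. SAP 9.4.1 lists the endpoints at Weeks 4, 8, 12 and 16. The schedule of assessments also collects EASI, vIGA, BSA, SCORAD, POEM and DLQI at Week 2, and Protocol 11.6 describes repeated-measures models "with all time points collected for the relevant endpoint included in the model". Week 2 is therefore probably in the model, which would make five visits.

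Neither document gives a standard deviation, a baseline-to-visit correlation or a power figure for any continuous endpoint.

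**The concern.** A participant with high baseline EASI has more room to improve in absolute terms. If improvement is roughly proportional to baseline, the slope of absolute change on baseline is about minus the mean fractional improvement. That slope is near zero early and steeper at Week 16. The design gives some reason to expect this. The primary endpoint is itself a proportional reduction, and the protocol's amendment history justifies the move from 12 to 16 weeks by a greater chance of benefit with longer treatment.

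With an unstructured covariance, a single slope is estimated mainly from the visits with the least residual variation, usually the early ones. Week 16 then receives too little baseline adjustment, and its residual variance is larger than it need be. What is at stake is the width of the Week 16 confidence intervals for the eight absolute-change analyses in SAP 9.4.1. The other six of the 14 are percentage changes. This deserves attention because SAP 7.6 puts the focus of the study on estimating treatment effects.

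**Working it through.** **1. The plan's own figure.** The only sample-size figure is for the binary primary endpoint: 25% versus 50%, two-sided 5%, 80% power.

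n = [1.96·√(2·0.375·0.625) + 0.8416·√(0.25·0.75 + 0.5·0.5)]² / 0.25² = (1.342 + 0.557)² / 0.0625 ≈ 57.7, so 58 per group. Power at 58 is 80.2%. With 20% drop-out, 58/0.8 = 72.5, so 73.

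The plan's figures reproduce, but they say nothing about MMRM precision.

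**2. Cost in parameters.** With five visits, baseline score*visit adds (5 − 1) × 1 = 4 and vIGA*visit adds (5 − 1) × 2 = 8, in total 12. With four visits the total is 3 × (1 + 2) = 9. Cohorts 1–3 randomise 300 ("With 75 EDP1815 participants and 25 placebo participants in each of the three cohorts").

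**3. Large-sample formula, complete data.** Let β be the vector of visit-specific slopes on baseline and R the residual covariance given baseline. The fitted common slope is

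b = (1′R⁻¹β) / (1′R⁻¹1).

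The Week 16 standard error with the interaction, relative to without it, is

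√{ R₁₆ / [R₁₆ + (β₁₆ − b)²·var(baseline)] }.

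Working with change rather than score lowers every slope by 1 and leaves β₁₆ − b unchanged.

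*Worked case (assumed).* Constant SD of 1, first-order autoregressive correlation of 0.90 per 4 weeks, visits at Weeks 2, 4, 8, 12 and 16. Then β = (0.949, 0.900, 0.810, 0.729, 0.656), b = 0.932 and R₁₆ = 1 − 0.656² = 0.570. The ratio is √[0.570 / (0.570 + 0.275²)] = 0.939, a 6.1% reduction.

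| Assumed correlation, constant SD | Week 2 included | Week 2 left out |
|---|---|---|
| Compound symmetry | 0.0% | 0.0% |
| AR, 0.95 per 4 weeks | 3.4% | 2.4% |
| AR, 0.90 | 6.1% | 3.9% |
| AR, 0.80 | 9.2% | 5.2% |
| AR, 0.70 | 9.8% | 4.8% |

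Letting the SD change widens the range. With Week 2 included, an SD falling to 0.8 of baseline under AR 0.80 gives 13.5%. An SD rising to 1.4 times baseline under AR 0.90 gives 0.5%.

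**4. Simulation with drop-out.** Four groups of 75, five visits, 20% random drop-out, three-level vIGA, 120 runs per setting, model-based standard errors. The reductions were −0.5% (compound symmetry 0.6, a small loss), 5.4% (AR 0.90), 6.7% (random intercept 0.3 plus AR 0.7), 8.6% (AR 0.80) and 9.9% (AR 0.70). Empirical standard errors from 120 runs were too noisy to use.

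**5. Proportional improvement.** One simulation took skewed baseline EASI, mean improvement rising from 10% to 40%, four arms of 58 and about 6% drop-out per visit.

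- Absolute change, empirical: 1.035/1.103 = 0.938, a 6.2% reduction.
- Absolute change, model-based: 1.075/1.132 = 0.950, a 5.0% reduction.
- Percentage change: 6.260/6.268 = 0.999, in effect none.

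The 58 per arm is the number before inflation for drop-out, so this setting counts drop-out twice; the effect on the ratio is probably small. Large-sample calculations under other proportional-improvement paths gave about 0.2–8.5% with Week 2 and 0.1–3.6% without it.

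**6. Carry-forward.** Under EDPS1, a continuous value within 28 days of rescue, or missing after a treatment-related withdrawal, is replaced by the last off-rescue value. Carrying early values to Week 16 flattens the growth in slope. With 20–35% of values carried forward (assumed), one set of reductions moved from 1.6–6.0% to 1.3–5.0%.

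**The case against.** The strongest reply is that the gain is assumed throughout. With constant baseline-to-visit correlation and constant SD there is no gain, and the extra terms cost a little. The gain shrinks, often by half or more, if Week 2 is left out, and carry-forward reduces it further. These are secondary endpoints with no multiplicity control and no power claim. All of that stands, and it limits the point to a low-cost refinement.

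Some stronger readings are tempting, but the documents do not support them:

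- *A saving of 5–6% can be counted on.* That figure belongs to one scenario. Its inputs are not in the protocol or SAP, and equally plausible inputs give anything from a slight loss to about 10%.
- *The terms are free.* They use 12 parameters and cost about 0.5% in standard error when slopes do not differ by visit.
- *The treatment estimates are biased, or the primary result is affected.* With randomisation and complete data, a common slope costs precision only. The primary analysis in SAP 9.3.3 is a logistic regression on Week 16 data alone.
- *All continuous endpoints lose precision.* Percentage change showed no effect. The scenario modelled on a named scale used EASI, so the extension to the other absolute-change endpoints is by analogy. The gain from vIGA*visit was not isolated from that of baseline score*visit.

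**Conclusion.** The point holds as a matter of efficiency. The specified MMRM constrains the baseline effects to be constant over visits while leaving the covariance free. Where improvement grows with time in proportion to baseline, that constraint costs precision at Week 16 for absolute change. A reasonable statement of size is a 0–10% reduction in standard error. A value near 13.5% was reached only by also assuming that the SD falls over time.

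The range depends on five things that the documents do not quantify for these endpoints: the improvement trajectory, the growth or decline of variance, the decay of correlation with baseline, whether Week 2 enters the model, and how much data is carried forward. The case for acting rests on the asymmetry between a worst loss of about 0.5% and plausible gains of several percent. It does not rest on any single figure.

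**What to change.** In SAP 9.4.1.2, add baseline score*visit and baseline vIGA*visit to the fixed effects, or give a reason for assuming constant baseline effects. In the same edit, state whether Week 2 is in the model. The Cohort 4 addendum takes its models from the main SAP, so the change carries over. That model has about 70 + 35 + 35 + 75 = 215 participants, and the cost above was worked out for 300.

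Make the change before the data concerned are unblinded. Cohorts 1–3 are planned to be locked and unblinded before the end of Cohort 4, so their deadline is earlier. If it has passed, report the extended model for those cohorts as a sensitivity analysis.

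The cost is one sentence in the SAP, two terms in the model statement and the 12 parameters. It needs no new data, visits or participants. The added fixed effects do not enlarge the covariance matrix, and the SAP's fallback to a simpler covariance structure remains available.

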9.4.2 Response Endpoints

The following endpoints will be analysed in the same manner as described below:

- Percentage of participants achieving EASI-50, EASI-75, EASI-90 at Weeks 4, 8, 12 and 16
- Percentage of participants achieving vIGA of 0 or 1 with a ≥ 2 -point improvement from baseline at Weeks 4, 8, 12 and 16
- Percentage of participants achieving vIGA of 0 or 1 at Weeks 4, 8, 12 and 16
- Percentage of participants achieving vIGA of 0 at Weeks 12 and 16
- Percentage of participants achieving BSA-50, BSA-75 at Weeks 4, 8, 12 and 16
- Percentage of participants achieving BSA reduction to 3% or less at Weeks 4, 8, 12 and 16
- Percentage of participants achieving SCORAD-35, SCORAD-50, SCORAD-75 at Weeks 4, 8, 12 and 16
- Percentage of participants achieving improvement of ≥ 4 points in DLQI score from baseline at Weeks 4, 8, 12 and 16
- Percentage of participants achieving improvement of ≥ 2 , ≥ 4 points in PP-NRS score from baseline at Weeks 4, 8, 12 and 16

- Percentage of participants achieving improvement of ≥ 2 points in SD-NRS score from baseline at Weeks 4, 8, 12 and 16
- Percentage of participants achieving improvement of ≥ 4 points in POEM score from baseline at Weeks 4, 8, 12 and 16
- Proportion of participants requiring TCS/TCI rescue therapy in periods Weeks 1-4, 5-8, 9-12, 13-16 and Weeks 1-16.

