7.1.2.1 Efficacy Data Point Set 1 (EDPS1)

EDPS1 consists of all data collected at a scheduled timepoint that is at least 28 days after use of TCS/TCI rescue therapy* or type 1 prohibited medication and before use of type 2 prohibited medication. Data collected less than 28 days after such use or data missing due to withdrawal from the study for reasons considered related to study medication** or data collected after use of type 2 prohibited medications will be replaced as follows:

- Continuous endpoints: value will be imputed with the last off-rescue¹ observation in the period before the event plus early termination visit in case of early study discontinuation (off-rescue is defined as data collected at least 28 days after use of rescue medication or type 1 prohibited medication)
- Responder endpoints: value will be imputed as non-response.
- Count endpoints: N/A (no count endpoint will use this DPS).

Data missing for other reasons, including early withdrawal from the study due to reasons not considered related to study medication will not be replaced and will be considered as missing.

Example 1: if patient completed 16 weeks of study with rescue therapy during week 3 and then during week 10 then responder endpoints will be analysed as shown in table:

Week 0	Week 2	Week 4	Week 8	Week 12	Week 16
As collected	As collected	Imputed as non-responder because there was a rescue therapy within 28 days before Week 4 visit	As collected	Imputed as non-responder because there was a rescue therapy within 28 days before Week 12 visit	As collected

Example 2: if patient completed 16 weeks of study with rescue therapy from Day 25 to Day 31 then responder endpoints will be analysed as shown in table:

Week 0	Week 2	Week 4	Week 8	Week 12	Week 16
As collected	As collected	Imputed as non-responder because there was a rescue therapy within 28 days before Week 4 visit	Imputed as non-responder because there was a rescue therapy within 28 days before Week 4 visit	As collected	As collected

Example 3: if patient withdrew study early due to the lack of efficacy after 12 weeks of treatment with rescue therapy during week 3 (unscheduled rescue therapy visit was not done) and then during week 10 (unscheduled rescue therapy visit was done at Week 9 prior to the rescue therapy start) then continuous endpoints will be analysed as shown in table:

Week 0	Week 2	Week 4	Week 8	Week 12	Week 16

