- Cohort 3 Placebo
- Cohort 3 EDP1815
- Cohort 4 Placebo (final analysis only)
- Cohort 4 EDP1815 (final analysis only)
- All Placebo
- All EDP1815
- Total

For cohorts 1-3 efficacy outputs, columns will be ordered and labelled as follows:

- All Placebo
- Cohort 1 EDP1815
- Cohort 2 EDP1815
- Cohort 3 EDP1815
- Cohorts 2+3 EDP1815
- All EDP1815

For cohort 4 efficacy outputs, columns will be ordered and labelled as follows:

- Cohort 4 Placebo
- Cohort 4 Matched Placebo
- Cohort 4 EDP1815
- Cohort 1 EDP1815

For concomitant medication and safety outputs, columns will be ordered and labelled as follows:

- All Placebo
- Cohort 1 EDP1815
- Cohort 2 EDP1815
- Cohort 3 EDP1815
- Cohort 4 EDP1815 (final analysis only)
- All EDP1815

For the analysis:

- For study disposition summaries where it is appropriate to report information on participants who failed screening, the enrolled population will be used.
- For safety summaries, where data is assigned to specific scheduled visits, the safety population with SDPS1 will be used.
- For safety summaries, where all other safety data is presented (including adverse events and worst-case change from baseline endpoints), the safety population with SDPS2 will be used.
- For the primary estimand and all secondary and exploratory estimands, full analysis population with EDPS1 will be used.
- For the supplementary estimands for the primary endpoint, full analysis population with EDPS2-EDPS5 will be used.
- Selected secondary response endpoints will also have secondary supplementary estimands: full analysis population with EDPS2 and EDPS6 will be used for endpoints based on EASI, vIGA and PP-NRS.
- For the secondary count endpoints, full analysis population with EDPS7 will be used.
- For the exploratory endpoints, full analysis population with EDPS1 will be used.
- For all other summaries and analyses the full analysis population will be used.

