9.4 Secondary Efficacy Analyses

All efficacy analysis details in this section are provided for cohorts 1-3 analysis.

For cohort 4 analysis the same approach will be used. Any differences and additional analyses will be described in the SAP Addendum.

All continuous and response secondary estimands will use EDPS1 (the primary estimand approach).

Secondary continuous and response endpoints based on the EASI, vIGA and PP-NRS will be analysed with a supportive estimands using EDPS2 (the supplementary estimand 1 approach) and EDPS6 for the response endpoints only (the supplementary estimand 5 approach).

Count secondary endpoints will use EDPS7 (estimand includes all data as collected prior to completion or withdrawal from the study).

The following treatment differences will be estimated:

- Cohort 1 EDP1815 vs Pooled placebo
- Cohort 2 EDP1815 vs Pooled placebo
- Cohort 3 EDP1815 vs Pooled placebo
- Cohorts 2+3 EDP1815 treatment group vs all placebo
- All EDP1815 treatment group vs all placebo
- Cohort 2 EDP1815 vs Cohort 3 EDP1815*
- Cohort 1 EDP1815 vs Cohort 2 EDP1815*

* Comparisons between EDP1815 treatment groups will be considered as exploratory analysis.

The comparisons between pooled EDP1815 groups and comparisons between EDP1815 treatment groups* will be done using contrasts (LSMESTIMATE statement) within the relevant SAS procedures.

Summary statistics only will be presented for Week 20 for those participants who completed treatment but did not wish to participate in the OLE.

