Version 2.0, Final 16-Jan-2023

EDP1815-207

Number	Title	Population	Data Point Set	Programming notes
14.2.26.1	Summary and Analysis of PP-NRS With a ≥ 4 Point Improvement from Baseline for Participants with a Score of ≥ 4 at Baseline - GLMM	FAS	EDPS1	
14.2.26.2	Summary and Analysis of PP-NRS With a ≥ 4 Point Improvement from Baseline for Participants with a Score of ≥ 4 at Baseline - GLMM	FAS	EDPS2	
14.2.26.3	Summary and Analysis of PP-NRS With a ≥ 4 Point Improvement from Baseline for Participants with a Score of ≥ 4 at Baseline - GLMM	FAS	EDPS6	
14.2.27.1	Summary of Absolute Change from Baseline in SD-NRS Score	FAS	EDPS1	
14.2.27.2	Analysis of Absolute Change from Baseline in SD-NRS Score - MMRM	FAS	EDPS1	
14.2.28	Summary and Analysis of SD-NRS With a ≥ 2 Point Improvement from Baseline for Participants with a Score of ≥ 2 at Baseline - GLMM	FAS	EDPS1	
14.2.29.1	Summary of Percentage Change from Baseline in POEM Score	FAS	EDPS1	
14.2.29.2	Analysis of Percentage Change from Baseline in POEM Score - MMRM	FAS	EDPS1	
14.2.30.1	Summary of Absolute Change from Baseline in POEM Score	FAS	EDPS1	
14.2.30.2	Analysis of Absolute Change from Baseline in POEM Score - MMRM	FAS	EDPS1	
14.2.31	Summary and Analysis of POEM With a ≥ 4 Point Improvement from Baseline for Participants with a Score of ≥ 4 at Baseline - GLMM	FAS	EDPS1	Include in TLR
14.2.32.1	Summary of Number of Courses of Rescue Therapy	FAS	EDPS7	
14.2.32.2	Analysis of Number of Courses of Rescue Therapy – Poisson Regression	FAS	EDPS7	
14.2.33.1	Summary of Days with Rescue Therapy	FAS	EDPS7	
14.2.33.2	Analysis of Days with Rescue Therapy – Poisson Regression	FAS	EDPS7	
14.2.34	Summary and Analysis of Requirement for Rescue Therapy - GLMM	FAS	EDPS7	
14.2.35	Summary of Time to First Achievement of EASI-50 Response	FAS	EDPS1	
14.2.36	Summary of Time to First Achievement of Sustained EASI-50 Response	FAS	EDPS1	
14.2.54	Summary of Time to First Achievement of EASI-75 Response	FAS	EDPS1	
14.2.37	Summary of Time to First Achievement of vIGA of 0 or 1 with a ≥ 2 Point Improvement from Baseline	FAS	EDPS1	
14.2.55	Summary of Time to First Achievement of vIGA of 0 or 1	FAS	EDPS1	

Number	Title	Population	Data Point Set	Programming notes
14.2.38	Summary of Time to First Achievement of PP-NRS Score with a ≥ 2 Point Improvement from Baseline for Participants with a Score of ≥ 2 at Baseline	FAS	EDPS1	

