14.2.28.1	Proportion (95% CI) of Participants Achieving SD-NRS With a ≥ 2 Point Improvement from Baseline for Participants with a Score of ≥ 2 at Baseline at Week 16	FAS	EDPS1	
14.2.28.2	Adjusted Odds Ratio (95% CI) for Achievement of SD-NRS With a ≥ 2 Point Improvement from Baseline for Participants with a Score of ≥ 2 at Baseline - GLMM	FAS	EDPS1	
14.2.30.1	Waterfall Plot of Absolute Change from Baseline in POEM Score at Week 16	FAS	EDPS1	
14.2.30.2	LS Mean (95% CI) Absolute Change from Baseline in POEM Score - MMRM	FAS	EDPS1	
14.2.30.3	LS Mean Difference (95% CI) in Absolute Change from Baseline in POEM Score - MMRM	FAS	EDPS1	
14.2.31.1	Proportion (95% CI) of Participants Achieving POEM With a ≥ 4 Point Improvement from Baseline for Participants with a Score of ≥ 4 at Baseline at Week 16	FAS	EDPS1	Include in TLR
14.2.31.2	Adjusted Odds Ratio (95% CI) for Achievement of POEM With a ≥ 4 Point Improvement from Baseline for Participants with a Score of ≥ 4 at Baseline GLMM	FAS	EDPS1	
14.2.32	Histogram of Number of Courses of Rescue Therapy	FAS	EDPS7	
14.2.34.1	Proportion (95% CI) of Participants Not Requiring for Rescue Therapy on or before Week 16	FAS	EDPS7	
14.2.34.2	Adjusted Odds Ratio (95% CI) for Not Requiring for Rescue Therapy - GLMM	FAS	EDPS7	
14.2.35	Cumulative Incidence (95% CI) of EASI-50	FAS	EDPS1	

Statistical Analysis Plan
Version 2.0, Final 16-Jan-2023

EDP1815-207

Number	Title	Population	Data Point Set	Programming notes
14.2.36	Cumulative Incidence (95% CI) of Sustained EASI-50	FAS	EDPS1	
14.2.54	Cumulative Incidence (95% CI) of EASI-75	FAS	EDPS1	
14.2.37	Cumulative Incidence (95% CI) of IGA of 0 or 1 with a ≥ 2 Point Improvement from Baseline	FAS	EDPS1	
14.2.55	Cumulative Incidence (95% CI) of IGA of 0 or 1	FAS	EDPS1	
14.2.38	Kaplan-Meier Survival Curve for Time to First Achievement of PP-NRS Score with a ≥ 2 Point Improvement from Baseline for Participants with a Score of ≥ 2 at Baseline	FAS	EDPS1	
14.2.39	Kaplan-Meier Survival Curve for Time to First Achievement of PP-NRS Score with a ≥ 2 Point Sustained Improvement from Baseline for Participants with a Score of ≥ 2 at Baseline	FAS	EDPS1	
14.2.40	Kaplan-Meier Survival Curve for Time to First Achievement of PP-NRS Score with a ≥ 4 Point Improvement from Baseline for Participants with a Score of ≥ 4 at Baseline	FAS	EDPS1	

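### The secondary rescue endpoint was reversed to 'requiring rescue', but the SAP text leaves it on EDPS1, where imputed non-response now means 'not requiring'; the output list names EDPS7, with no stated value for participants who leave without rescue

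*SAP*

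**What the plan says.** **Endpoint.** Protocol Table 11-2 has absence of a need for rescue as a response endpoint. Protocol 11.3.2 puts response endpoints on EDPS1, and 11.1.2 limits EDPS7 to count endpoints. SAP 9.4.2 models the reverse: "Proportion of participants requiring TCS/TCI rescue therapy in periods Weeks 1-4, 5-8, 9-12, 13-16 and Weeks 1-16". SAP 13 logs that reversal, explained as easier interpretation, and the restriction to TCS/TCI rescue.

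**Data point set in the text.** SAP 9.4: "All continuous and response secondary estimands will use EDPS1 (the primary estimand approach"). SAP 8: "For the primary estimand and all secondary and exploratory estimands, full analysis population with EDPS1 will be used". Among the secondaries, the text exempts only counts: "For the secondary count endpoints, full analysis population with EDPS7 will be used".

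**EDPS1 rule.** SAP 7.1.2.1 replaces data collected less than 28 days after rescue or type 1 medication, data missing through related withdrawal, and data after type 2 medication. For binary endpoints: "Responder endpoints: value will be imputed as non-response".

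**Data point set in the outputs.** SAP 15.2.1 lists Table 14.2.34, "Summary and Analysis of Requirement for Rescue Therapy - GLMM", on EDPS7. SAP 15.2.2 lists Figure 14.2.34.1, "Proportion (95% CI) of Participants Not Requiring for Rescue Therapy on or before Week 16", and Figure 14.2.34.2, "Adjusted Odds Ratio (95% CI) for Not Requiring for Rescue Therapy - GLMM", also on EDPS7.

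**Derivation.** SAP 5.3.3.14 counts a participant as a rescue user in any period that a course overlaps. SAP 7.1.2.7 ends EDPS7 collection at study discontinuation.

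**The concern.** The protocol's event was the good outcome, so imputed non-response meant that rescue was required. Once the event becomes the bad outcome, the same imputation wording gives the good value. The SAP changed the event without restating the imputation. EDPS1 also treats recent rescue as an intercurrent event, although rescue is what this endpoint measures. Protocol 11.3.2 says rescue is not an intercurrent event, but only for count endpoints.

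Two programmers, one following the text and one the output list, would analyse different data for the same odds ratio and p-value. The one following the output list would still have to choose a value for participants who leave without rescue.

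**Working it through.** The plan states no figure for this endpoint, so the check compares passages; the arithmetic is illustrative.

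**1. Direction.** SAP 9.4.2.1 defines the odds ratio for achieving response, and 9.4.2.2 reports responders in each period. The modelled event is therefore the response.

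| | Protocol event: no rescue required | SAP event: rescue required |
|---|---|---|
| Imputed non-response means | required rescue (unfavourable) | did not require rescue (favourable) |

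The protocol's composite covers recent rescue and related withdrawal. Adding type 2 medication to it is the SAP's own change (SAP 13); protocol 11.3.2 used treatment policy for prohibited medication.

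**2. Conflict with the derivation.** SAP 5.3.3.14 codes any overlapping course as use. EDPS1 would recode some of that use as non-use. How much depends on an assumption: EDPS1 refers to scheduled timepoints and the SAP does not link periods to visits. Suppose Weeks 13-16 are Days 85-112 and the status is read at the Week 16 visit on Day v. Use on Day d < v is recoded if v − d < 28.

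| v | Days recoded | Of 28 |
|---|---|---|
| 110 | 85-109 | 25 |
| 113 | 86-112 | 27 |
| 116 | 89-112 | 24 |
| 117 | 90-112 | 23 |

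Days 110 to 116 are the Day 113 ± 3 window of protocol Table 4-1. Day 117 arises because protocol 7.7 sets the visit 113 days after Day 1, which is Day 114 ± 3. On this reading nearly all rescue use in the period would itself trigger the imputation. That shows the circularity; it does not estimate the effect.

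**3. Gap under EDPS7.** Rescue before exit is coded as use by SAP 5.3.3.14. For withdrawal without rescue, nothing states the value in the cut-short period or in Weeks 1-16. The rule requiring a visit in the period and the log(days) offset, both in SAP 9.4.3.2, belong to the count models; the binary model in 9.4.2.2 has neither.

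**4. Sensitivity to the value chosen (all inputs assumed).** Let q be the rescue rate among other participants, equal in both arms, and w the share who leave for related reasons without rescue. The proportion requiring rescue is p = q(1 − w) + w·c, with c = 0 if leavers are coded not requiring and c = 1 if requiring; if they are missing, p = q. Planned drop-out is 20% (15 of 75 per arm), so w = 20% means that all drop-out is of this kind.

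For q = 30%, w = 20% placebo and 10% EDP1815:
- not requiring: 0.24 and 0.27; OR (0.27/0.73)/(0.24/0.76) = 1.17
- missing: 0.30 and 0.30; OR 1.00
- requiring: 0.44 and 0.37; OR (0.37/0.63)/(0.44/0.56) = 0.75

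| w placebo, EDP1815 | Not requiring | Missing | Requiring |
|---|---|---|---|
| 20%, 10% (q = 20-40%) | 1.15-1.20 | 1.00 | 0.69-0.79 |
| 10%, 5% (q = 20-40%) | 1.07-1.09 | 1.00 | 0.81-0.89 |
| 10%, 10% (q = 20-40%) | 1.00 | 1.00 | 1.00 |

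With equal w only the level moves (q = 30%, w = 10%: 27%, 30%, 37%). These ratios concern withdrawals only; they do not measure the recoding in step 2.

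**5. Table against figures.** The table models requirement and the figures are titled for its absence. As titled, the plotted odds ratios would be reciprocals of those tabulated.

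**The case against.** The strongest reply is that EDPS7 is what will be run. The table and both figures name it, SAP 7.1.2.7 dropped the protocol's restriction to counts, and SAP 9.5.1 already gives EDPS7 to exploratory response subgroup endpoints. EDPS1 is worded for scheduled timepoints and fits a period endpoint poorly, a misfit already present in the protocol. The specific rule in SAP 5.3.3.14 should outrank a generic sentence. The SAP never defines response for this endpoint, so the log entry could be read as changing only the modelled event. Under EDPS7, ending collection at discontinuation suggests judging status over observed time, and protocol 11.6 leaves missing data unimputed by default.

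Much of this stands. EDPS7 is evidently intended, and rescue before exit does have a value. What remains is that SAP 8 and 9.4 say otherwise without exception, that 9.4.2.1 and 9.4.2.2 treat the modelled event as the response, and that status over observed time is one plausible reading among several, not a written rule.

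Two stronger inferences are tempting. One is that the reversal biases the result towards EDP1815. The documents do not support this: the literal coding helps whichever arm has more related withdrawals without rescue, and in step 4 it works against EDP1815. The other is that most rescue use will be overwritten. That needs the closing-visit reading of step 2, which appears nowhere in the documents.

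**Conclusion.** The SAP is wrong as written for this one secondary endpoint. Its text and its output list name different data point sets, and the text rule, taken literally, gives the favourable value to participants whom the protocol's composite would count as requiring rescue. EDPS7 resolves most of this but leaves withdrawal without rescue open. SAP 13 does not record the change of data point set.

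Confidence is high on the mismatch, the stale figure titles and the missing rule. The favourable direction rests on reading the modelled event as the response. The effect on the odds ratio cannot be derived; under assumed inputs it is nil with balanced related withdrawals and material with unbalanced ones. The stakes are limited: the endpoint is one of many secondaries without multiplicity adjustment, its outputs are not marked for top-level results, and offset-adjusted counts of courses and days are analysed beside it. It should be corrected.

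**What to change.** 1. In SAP 8 and 9.4, except this endpoint from EDPS1 and assign EDPS7, matching the output list.
2. State that rescue is the outcome here and not an intercurrent event, and that EDPS1 non-response imputation does not apply.
3. State that any course overlapping a period, or Weeks 1-16, counts as requiring rescue.
4. State one value for withdrawal without rescue. For example, set periods not reached, and incompletely observed periods without rescue, to missing, and apply the same rule to Weeks 1-16. Optionally add a sensitivity analysis counting related withdrawals as requiring rescue, which keeps the protocol's direction.
5. Log the change of data point set in SAP 13.
6. Retitle Figures 14.2.34.1 and 14.2.34.2 to the modelled direction.

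The cost is a few sentences, one derivation flag and two titles, plus one extra row if the sensitivity analysis is added. Setting only leavers without rescue to missing keeps those who used rescue before leaving, so it raises the reported proportion somewhat. The optional analysis measures rescue or treatment-related withdrawal combined and should be labelled so.
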